#### **2.4.4 Analyses of efficacy endpoints**

##### ***2.4.4.1 Analysis of primary efficacy endpoint(s)***

Not applicable.

##### ***2.4.4.2 Analyses of secondary efficacy endpoints***

Efficacy variables will be analyzed in the mITT population through descriptive statistics. No formal statistical comparisons will be performed for efficacy variables.

Quantitative descriptive summaries (number of available data, mean, SD, median, Min and Max) by planned time points will be presented for all lipids using observed (ie, non-missing) data. Missing data will not be imputed. In addition, standard error (SE) and the 95% CI for the mean will be provided for lipids other than TGs and Q1 and Q3 will be provided for TGs. The computation of the 95% CI will be based on a normal distribution or a Student distribution depending on the number of patients.

For all continuous secondary efficacy endpoints (LDL-C, non-HDL-C, total-C, HDL-C and triglycerides), percent changes from baseline using number of available data, mean, SD, median, Min, and Max will be displayed. For percent changes, 95% CI of the mean will also be provided.

The proportions of patients reaching the different targets defined for LDL-C (see [Section 2.1.3.2](#)) will be provided with their corresponding 95% CI. In case of a number of patients deemed insufficient, the Clopper-Pearson algorithm will be used to compute the 95% CI.

All measurements, scheduled or unscheduled will be assigned to analysis windows defined in [Section 2.5.4](#).

Regarding the patterns of up-titration/down-titration, the proportions with their corresponding 95% CI, will be provided for the following categories:

- Patients with at least one up-titration to 150 mg of alirocumab during the observational period. The time from the initiation of alirocumab at 75 mg to the first up-titration to 150 mg will be quantitatively described and the reasons that triggered the change of dosage will be displayed (AE, Lipid values or others).
- Patients with at least one down-titration to 75 mg of alirocumab during the observational period. The time from the initiation of alirocumab at 150 mg to the first down-titration to 75 mg will be quantitatively described and the reasons that triggered the change of dosage will be displayed (AE, Lipid values or others).
- Patients with a dose of alirocumab unchanged at 75 mg during the observational period and the duration of treatment without changes of doses.
- Patients with a dose of alirocumab unchanged at 150 mg during the observational period and the duration of treatment without changes of doses.

In addition, the number and the proportion of patients for which the dose of alirocumab was down-titrated back to 75 mg and for which the dose of alirocumab was up-titrated back to 150 mg will be described.

The last LDL-C value prior to the up-titration/down-titration or prior to the initiation of treatment for patients with a dose unchanged throughout the study will be summarized quantitatively and with the following categories: <15,  $\geq 15$  and <25,  $\geq 25$  and <50,  $\geq 50$  and <70,  $\geq 70$  and <100,  $\geq 100$  mg/dL. The LDL-C value at least 4 weeks after up-titration/down-titration will also be provided for patients without any additional change of dosage (LDL-C value selected will be the value nearest to the date of titration + 28 days). The 95% CI will be provided. In case of a number of patients deemed insufficient, the Clopper-Pearson algorithm will be used to compute the 95% CI.

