## 8 STUDY TREATMENTS

### 8.1 INVESTIGATIONAL MEDICINAL PRODUCT(S)

Sterile alirocumab drug product will be supplied at a concentration of 75 mg/mL and 150 mg/mL in histidine, pH 6.0, polysorbate 20, both as 1 mL volume in an auto-injector (also known as pre-filled pen).

Patient (or another designated person) will have to perform during the screening period (V1 or dedicated V2) or at the latest on V3 (Day 1) a placebo self-injection training, using a pre-filled pen, before the first alirocumab administration.

Injection for training: sterile placebo for alirocumab will be prepared in the same formulation as alirocumab without the addition of protein as 1 mL volume in a pre-filled pen, for the patients to perform an injection training.

Each alirocumab administration will consist of 1mL subcutaneous injection over the abdomen, thigh, or outer area of upper arm (ie, deltoid region).

The recommended dose is 75 mg or 150 mg administered subcutaneously once every 2 weeks (Q2W).

The dose selection should be based on individual patient characteristics and goal of therapy.

The dose can be adjusted based on treatment response. Lipid levels will be analyzed from Week 4, when maximum LDL-C reduction is usually achieved.

The Investigator is free to adjust the dose (up and down-titration) throughout the study based on clinical judgment.

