### **Blood samplings:**

The blood samplings including the determination of lipid parameters (ie, total-C, LDL-C, HDL-C, TG, non-HDL-C, FPG and HbA1C) should be performed in the morning, in fasting condition (ie, overnight, at least 10 to 12 hours fast and refrain from smoking), and before IMP injection for all site visits throughout the study. Alcohol consumption within 48 hours and intense physical exercise within 24 hours preceding the blood sampling are discouraged.

*Note: if the patient is not in fasting conditions, the blood sample will not be collected and a new appointment will be given the day after (or as close as possible to this date) to the patient with instruction to be fasted (see above conditions) and not having taken IMP (injection to be delayed accordingly).*

In case the lipid results are made available during the visit, the lipid results performed at local laboratory will be reviewed at the on-site visit by the investigator, and, in case a dose adjustment is required, the dose will be modified immediately or the patient will be requested to come to the site within a few days for an unscheduled visit, so that the dose can be adjusted as needed.

The unscheduled dispensation visit will be similar to the “dispensation only” visits, eg, V10/W36.

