### **Laboratory tests:**

The laboratory data are collected in accordance with the study schedule in [Section 1.2](#) and forwarded to the local Laboratory:

- Hematology: (all site visits except V2, V3/inclusion, V6/W8, dispensation visits and EOT/EOS: see [Section 9.2](#) for details).
- Chemistry: (all site visits except V2, V3/inclusion, V6/W8, dispensation visits, EOT/EOT): see [Section 9.2](#) for details.
- Lipid profile: (screening, Week 4, Week 8, Week 12, Week 24, Week 48, Week 72, Week 96, and EOT/EOS): see [Section 9.2.1.1.1](#).
- Liver panel: in case of total bilirubin values above the normal range, differentiation into conjugated and non-conjugated bilirubin will occur automatically (screening, Week 4, Week 8, Week 12, Week 24, Week 48, Week 72, Week 96, EOT/EOS): see [Section 9.2](#) for details.
- Hepatitis B surface antigen (screening).

- Hepatitis C antibody, at screening and EOT/EOS; in case of ALT increase during the study, hepatitis C antibody should be determined and if positive a reflexive testing should be performed).
- Serum pregnancy test (screening only).
- Urine pregnancy test (inclusion and EOT/EOS).

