#### **10.1.2.3 Visit 5 / Week 4 (Day 29 ±3), Visit 6 / Week 8 (Day 57 ±3), Visit 7 / Week 12 (Day 85 ±3), Visit 9 / Week 24 (Day 169 ±5), Visit 11 / Week 48 (Day 337 ±7), Visit 13 / Week 72 (Day 505 ±7), Visit 15 / Week 96 (Day 673 ±7)**

During these visits the below will be performed:

- Collect AEs.
- Check product complaints.
- Check compliance on IMP (review patient diary and treatment kit) and data collection on IMP administration.
- Record concomitant medication.
- Perform physical examination.
- Take vital signs including HR and BP.
- Urinalysis (only at V7).
- Laboratory tests: Hematology, Biochemistry, Liver panel, Lipid profile (hematology and biochemistry not needed for V6), HbA1c (except at V5 and V6).

- Remind Nutritional Counseling (including reviewing patient's diet).
- Provide any injection training reminder as needed.
- IVRS contact for treatment kit dispensing (at V5 and V6, new treatment kit dispensing would be done as per titration needs).

Reminders:

- An appointment will be given for the next study site visit, to be done before next IMP administration.
- Remind patient to be in fasting conditions (ie, overnight, at least 10 to 12 hours fast and refrain from smoking) for next study site visit. Also, alcohol consumption within 48 hours and intense physical exercise within 24 hours preceding the next study site visit are discouraged.
- Ask the patient to complete the SIAQ POST (ie, after alirocumab injection).
- Patient to bring the diary to the next study site visit.
- If upon review of the laboratory blood test results, the investigator judges that a dose titration of the patient dose is necessary, then he/she will contact the patient and plan an unscheduled visit. The assessments of the unscheduled visit will be at minimum the same of the "dispensation only" visit (eg, V10/Week 36).

**10.1.2.4 Dispensation visits: Visit 10 / Week 36 (Day 253 ±7), Visit 12 /Week 60 (Day 421 ±7), Visit 14 / Week 84 (Day 589 ±7), Visit 16 / Week 108 (Day 757 ±7)**

During dispensation visits the below will be performed:

- Treatment compliance will be checked.
- Patient' diaries will be reviewed.
- Safety and concomitant medication will be reviewed.
- Check product complaints.
- Provide any injection training reminder as needed.
- Treatment kit dispensing.

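### The summary of LDL-C after a dose change leaves out patients whose dose was changed again, and does not pin down when the sample is taken

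*SAP*

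**What the plan says.** SAP 2.4.4.2 gives the rule in one sentence: "The LDL-C value at least 4 weeks after up-titration/down-titration will also be provided for patients without any additional change of dosage". The parenthesis that follows adds: "LDL-C value selected will be the value nearest to the date of titration + 28 days". The SAP does not say whether the nearest value may fall before day 28, how far from day 28 it may lie, or whether an additional change counts at any time or only before the selected sample.

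The same section counts patients titrated back in either direction and lists lipid values among the recorded reasons for a change. Protocol 6.1 lets the investigator adjust the dose on clinical judgement and LDL-C.

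The sampling schedule is in Protocol 10 (Laboratory tests): "Lipid profile: (screening, Week 4, Week 8, Week 12, Week 24, Week 48, Week 72, Week 96, and EOT/EOS". The early visits carry a window of 3 days either way: "Visit 5 / Week 4 (Day 29 ±3), Visit 6 / Week 8 (Day 57 ±3), Visit 7 / Week 12 (Day 85 ±3". If the laboratory result leads to a dose change, Protocol 10.1.2.3 says of the investigator: "then he/she will contact the patient and plan an unscheduled visit". Protocol 10 (Blood samplings) allows an immediate change when results are at hand; otherwise "the patient will be requested to come to the site within a few days for an unscheduled visit". Protocol 8.1 gives the likely reason for a four-week interval: "Lipid levels will be analyzed from Week 4, when maximum LDL-C reduction is usually achieved".

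**The concern.** Whether a patient appears in this summary depends on something that happens after the value of interest and partly because of it. There are only two doses, so a further change after down-titration is a step up, and after up-titration a step down. Where lipids drive that change, the rule tends to remove the highest values after down-titration and the lowest after up-titration. The patients left would make down-titration look less costly in LDL-C than it was.

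Separately, two programmers could follow the sentence faithfully and select different samples for the same patient. This is the planned summary of LDL-C specifically after a dose change. The by-visit lipid summaries are not split by titration status, so they do not replace it.

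**Working it through.** The plan states no figure to reproduce here. The check applies the rule to the protocol's own schedule.

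**Inputs.** Nominal lipid days are 29, 57, 85, 169, 337, 505 and 673 (Protocol 1.2 and 10). EOT/EOS and unscheduled samples are left out because their dates are not fixed. The lag from triggering sample to dose change is 0, 3, 7 or 14 days, an assumed range, since the protocol says only immediately or within a few days. Titration day = trigger day + lag; target = titration day + 28. For ties, the later value is taken, by analogy with SAP 2.5.4.

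**Selection, by example.** A patient is down-titrated on Day 32 (Week 4 sample + 3). The Day 57 sample, 25 days later, shows a rise, and the dose goes back up on Day 60. A post-titration value exists before the second change, yet the patient contributes nothing.

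**Selection, scale only.** If a share f of titrated patients is removed wholly from one tail of a normal distribution, the mean moves by SD × φ(z_f)/(1 − f), where φ is the standard normal density and z_f its f quantile. This is the most that excluding a share f can do.

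| f (assumed) | Shift in SD | SD 30 mg/dL | SD 42.6 mg/dL |
|---|---|---|---|
| 2% | 0.05 | 1.5 | 2.1 |
| 5% | 0.11 | 3.3 | 4.6 |
| 10% | 0.20 | 5.8 | 8.3 |
| 20% | 0.35 | 10.5 | 14.9 |

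The 42.6 is the baseline SD in the alirocumab arm of the long-term study described in Protocol 4; the 30 is an assumption. Neither is a post-titration SD.

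**Timing.** Reading A takes the value nearest the target among those at least 28 days after titration. Reading B takes the nearest post-titration value on either side of the target.

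| Trigger | Lag | Titration day | Target | Reading B | Reading A |
|---|---|---|---|---|---|
| Week 4 (Day 29) | 0 | 29 | 57 | Day 57, 28 d | Day 57, 28 d |
| | 3 | 32 | 60 | Day 57, 25 d | Day 85, 53 d |
| | 7 | 36 | 64 | Day 57, 21 d | Day 85, 49 d |
| | 14 | 43 | 71 | Day 85, 42 d (tie) | Day 85, 42 d |
| Week 8 (Day 57) | 0 | 57 | 85 | Day 85, 28 d | Day 85, 28 d |
| | 3 | 60 | 88 | Day 85, 25 d | Day 169, 109 d |
| | 7 | 64 | 92 | Day 85, 21 d | Day 169, 105 d |
| | 14 | 71 | 99 | Day 85, 14 d | Day 169, 98 d |
| Week 12 (Day 85) | 0–14 | 85–99 | 113–127 | Day 169, 84–70 d | same |
| Week 24 (Day 169) | 0–14 | 169–183 | 197–211 | Day 337, 168–154 d | same |
| Week 48 (Day 337) | 0–14 | 337–351 | 365–379 | Day 505, 168–154 d | same |

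**Visit windows.** Let the Week 4 and Week 8 visits each move by −3 to +3 days, giving 7 × 7 = 49 combinations, equally weighted. The Week 8 sample falls short of 28 days after a Week 4-triggered change in 21/49 (43%) at lag 0, 39/49 (80%) at lag 3 and 49/49 (100%) at lag 7.

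**The case against.** The strongest reply is that the sentence is coherent: the main clause sets eligibility at four weeks or more, and the parenthesis picks the eligible value closest to day 28. That reading is available, so a reader who infers a contradiction goes too far. The wording is ambiguous. The two readings also agree at zero lag on nominal days and for triggers at Week 12 or later.

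A reader might also infer that the rule can select the triggering sample itself. With titration on Day 88 the target is Day 116; Day 85 is 31 days away and Day 169 is 53. But the text requires a value after titration, so Day 85 is not eligible.

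A third tempting inference concerns patients whose dose never changed, where the value "prior to the initiation of treatment for patients with a dose unchanged throughout the study will be summarized". Every entry group requires LDL-C of at least 100 mg/dL, so nearly all should fall in the top category. Still, the SAP defines no comparison with titrated patients and plans a quantitative summary alongside the categories. It is not fair to say that summary carries no information.

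It is also true that re-titrated patients are counted, that this rule does not remove them from the by-visit LDL-C results, that the named titration endpoints are proportions and reasons, that nothing here is tested, and that unscheduled or EOT/EOS samples may fall nearer to day 28. All of this limits the reach of the point. None of it removes the conditioning on a later dose change or supplies the missing bounds.

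**Conclusion.** The point holds for one descriptive summary. Read literally, the restriction selects patients on a later event that LDL-C itself can drive. The likely direction is to understate the rise after down-titration. The size cannot be stated, because the documents give neither the share re-titrated nor the post-titration SD; the tail figures above show scale under assumed values only.

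The timing is under-specified. At an assumed 3-day lag the choice of reading moves the sample from 25 to 53 days (Week 4 trigger) or from 25 to 109 days (Week 8 trigger). With no upper limit, the only scheduled value is 70 to 84 days after a Week 12 trigger and 154 to 168 days after a Week 24 or Week 48 trigger, unless an unscheduled or EOT/EOS sample exists. No primary or key secondary endpoint is affected.

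**What to change.** Replace the sentence in SAP 2.4.4.2 with: *For all patients with a titration, the LDL-C value taken after the first titration and on or before the date of any further dose change, nearest to titration + 28 days within a stated window (for example 14 to 42 days), will be summarised. Later values before any further change will be shown separately. Days from titration to sample and the number of patients without a value will be reported.* State the tie rule as well. Delete the four-week minimum. Delete the restriction to patients with no further change, or keep it only as a sensitivity summary.

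A strict 28-day minimum should not be kept. In the example above, a Day 32 change would be eligible only from Day 60, so the Day 57 sample that prompted the reversal would still be lost. Counting from the first injection at the new dose (Day 43 on the nominal two-weekly schedule) would move eligibility to Day 71.

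The cost is SAP wording and programming; the dates needed are already collected. Some values will be taken before day 28, which the reported days since titration make visible. Patients titrated at Week 12 or later without an unscheduled or EOT/EOS sample in the window will appear only in the separate display of later values.

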#### **2.4.4.3 Multiplicity issues**

Not applicable.

#### **2.4.4.4 Additional efficacy analyses**

##### ***Occurrence of very low LDL-C level***

A LDL-C level <25 mg/dL (0.65 mmol/L) will be defined as very low. An alternative definition with a cut-off at 15 mg/dL (0.39 mmol/L) will also be used.

For each definition of very low LDL-C level, the number and percentage of patients who had a very low LDL-C level at least once during the observational period will be provided overall, by the LDL-C level at baseline (<70 mg/dL (1.81 mmol/L),  $\geq 70$  mg/dL and <100 mg/dL (2.59 mmol/L),  $\geq 100$  mg/dL and <130 mg/dL (3.37 mmol/L),  $\geq 130$  mg/dL and <160 mg/dL (4.14 mmol/L),  $\geq 160$  mg/dL) and by starting dose of alirocumab.

Among patients with a very low LDL-C level, the number and percentage of patients receiving each level of dose for alirocumab (75 mg and 150 mg) at the time of the corresponding LDL-C test will be provided. The time from the first injection of Alirocumab to the first occurrence of a very low value of LDL-C will also be displayed.

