## 1 OVERVIEW AND INVESTIGATIONAL PLAN

### 1.1 STUDY DESIGN

This trial is to be conducted as a multi-country, multi-center prospective, single arm, open-label, phase IIIb clinical trial.

After enrollment, patients received study treatment (alirocumab) 150 mg subcutaneous (SC) once every 2 weeks (Q2W) or 75 mg SC Q2W. The dose could be adjusted according to the investigator, based on treatment response.

Alirocumab was administered on top of stable maximally tolerated statin therapy ± other lipid modifying therapy (LMT) over a period of at least 12 weeks and until the product becomes commercially available and reimbursed but for a period not exceeding 30 months of treatment.

In each country, patient recruitment was scheduled to end when alirocumab became commercially available and reimbursed. In this case, study treatment could be switched to the commercial product (or another LMT) once the patient had completed the minimum of 12 weeks of study treatment. As a consequence, the total duration of study depend on countries with a minimum of 12 weeks in each participating country and the number of patients at each time point beyond 12 weeks of study treatment is likely to be very variable.

During the course of the study, the investigator managed, based on his/her own clinical judgment and low density lipoprotein cholesterol (LDL-C) value, adjustment of alirocumab doses (either up-titration from 75 to 150 mg Q2W or down-titration from 150 to 75 mg Q2W, or maintenance of the dose). In case a modification of the current dose was decided, the patient was contacted by the site staff and an unscheduled visit was planned to dispense the new treatment kit and retrieve the current one.

The study consists of:

- A screening period of up to 3 weeks, including a training injection during which the patient or another designated person (such as spouse, relative, etc) was trained to self-inject/inject. An optional dedicated visit could be scheduled as needed.
- An open-label treatment period with alirocumab of at least 12 weeks and until the product becomes commercially available and reimbursed. However, the open label treatment period cannot exceed 30 months.
- An end-of-treatment (EOT)/end-of-study (EOS) visit taking place at least 2 weeks after the last study treatment injection.

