Since the study duration for each participating country will depend on when alirocumab becomes commercially available and reimbursed, with a minimum duration of 12 weeks and up to a maximum of 120 weeks, the secondary efficacy endpoints associated to the lipid parameters will be also assessed at the following time points depending on countries: Weeks 4, 8, 12, 24, 48, 72, 96 and 120 (EOT/EOS).

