## 2.3 ANALYSIS POPULATIONS

### 2.3.1 Efficacy population

The efficacy population considered for efficacy analyses will be the mITT population.

The modified intent-to-treat population (mITT) also referred as on-treatment in section above, is defined as: all enrolled patients who took at least one dose or part of a dose of alirocumab and had an evaluable efficacy endpoint during the efficacy treatment period. The main efficacy endpoint will be evaluable provided that the 2 following conditions are met:

- Availability of a baseline calculated LDL-C value (last value available prior to the first injection of alirocumab).
- Availability of the calculated LDL-C within the analysis window associated to Week 12.

The efficacy treatment period is defined as the time period from the first injection of alirocumab up to the day of last injection + 21 days.

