### ***Analysis of all treatment-emergent adverse events***

The following TEAEs summaries will be generated for the safety population.

- Overview of TEAEs, summarizing number (%) of patients with any
  - Treatment-emergent adverse event,
  - Serious TEAE,
  - Treatment-emergent adverse event leading to death,
  - Treatment-emergent adverse event leading to permanent treatment discontinuation.
- All TEAEs by primary SOC, HLT, HLT, and PT.
- All TEAEs by primary SOC, HLT, HLT, and PT, showing number (%) of patients with at least 1 TEAE sorted by the SOC internationally agreed order. The other levels (HLT, HLT, PT) will be presented in alphabetical order.
- All TEAEs by primary SOC and PT, showing the number (%) of patients with at least 1 TEAE by primary SOC and PT, sorted by the internationally agreed SOC order and by decreasing incidence of PTs within each SOC. This sorting order will be applied to all other tables, unless otherwise specified.
- All TEAEs by PT, showing the number (%) of patients with at least 1 TEAE, sorted by decreasing incidence of PTs.
- All TEAEs regardless of relationship (in one column of the table) and related to alirocumab according to investigator's opinion (in a second column) by primary SOC, HLT, HLT and PT, showing the number (%) of patients with at least 1 TEAE, sorted by the internationally agreed SOC order. The other levels (HLT, HLT, PT) will be presented in alphabetical order.
- All TEAEs by maximal severity, presented by primary SOC and PT, showing the number (%) of patients with at least 1 TEAE by severity (ie, mild, moderate, or severe), sorted by the sorting order defined above.
- The event rate per patient-year (the number of patients with an event in question divided by total patient-years) will be provided for all TEAEs by SOC and PT. For a patient with event, patient year is censored at time of first event; for patient without event, it corresponds to length of TEAE period.
- Kaplan-Meier curves will be provided, when appropriate, for time from first dose of alirocumab to the first occurrence of selected TEAEs as well as incidence rates at 24 weeks of exposure. Patients without any event will be censored at the end of the TEAE period. Selected TEAEs will be all AESIs (as defined in [Section 2.1.4.1](#)).

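### Very low LDL-C is summarised as a crude ever/never percentage with no time reference, although follow-up and number of lipid tests differ widely between patients

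*SAP*

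**What the plan says.** SAP 2.4.4.4 defines very low LDL-C as below 25 mg/dL, with 15 mg/dL as an alternative cut-off. The summary is the number and percentage of patients "who had a very low LDL-C level at least once during the observational period", overall, by baseline LDL-C and by starting dose. The next paragraph, which opens by restricting itself to patients who had a very low value, adds: "The time from the first injection of Alirocumab to the first occurrence of a very low value of LDL-C will also be displayed". No censoring rule is given there. A later listing gives dates for the same patients.

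SAP 1.1 says treatment runs for at least 12 weeks and "until the product becomes commercially available and reimbursed but for a period not exceeding 30 months of treatment". For the lipid endpoints, SAP 2.1.3.2 instead describes follow-up "with a minimum duration of 12 weeks and up to a maximum of 120 weeks". SAP 1.1 also warns that "the number of patients at each time point beyond 12 weeks of study treatment is likely to be very variable".

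For other outcomes the plan does allow for unequal exposure. SAP 2.4.5.1 gives patient-year rates for all treatment-emergent adverse events and states: "Kaplan-Meier curves will be provided, when appropriate, for time from first dose of alirocumab to the first occurrence of selected TEAEs", the selected events being the adverse events of special interest. SAP 2.2 uses Kaplan-Meier for premature treatment discontinuation. Protocol 11.4.2.1 gives differing exposure time as the reason for its time-to-event analyses.

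**The concern.** An ever/never percentage cannot fall as tests accumulate, and here the number of tests is set largely by national reimbursement dates. The same drug effect gives a higher figure if late-reimbursing countries contribute more patients. The percentage has no time attached, so it cannot readily be set beside another study or beside a 12-week result.

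The splits by starting dose and baseline LDL-C inherit the problem if dose mix or case mix differs between early- and late-reimbursing countries. The documents do not show whether it does.

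The outcome matters. Protocol Section 4 says the safety of such low values is still being assessed, and notes more cataracts among alirocumab patients with two consecutive values below 25 mg/dL (2.1% against 0.6%). SAP 1.5 says the analyses were added to characterise these cases better.

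**Working it through.** **The plan's own figures.** None is given for very low LDL-C. The only design figures are the precision table and the rule of three at N = 1300, and both reproduce: for a 10% rate, 1.96 × √(0.10 × 0.90/1300) = 1.6 points, giving 8.4% to 11.6%; and 3/1300 = 0.23%.

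**Number of scheduled tests.** SAP 2.1.3.2 and Protocol Section 10 place post-baseline lipid profiles at Weeks 4, 8, 12, 24, 48, 72, 96 and the end-of-treatment visit.
- Full-length patient: 8.
- 12-week patient: 3, or 4 if the end-of-treatment sample is separate from Week 12. That visit falls 14 to 21 days after the last injection (Protocol 10.1.2.5), inside the efficacy treatment period, which ends 21 days after the last injection (SAP 2.3.1).
- Unscheduled values also count (SAP 2.1.3).

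The like-for-like comparison is 4 against 8, since the 8 includes the end-of-treatment test.

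**Model.** Let p be the chance that one test is very low, k the number of tests and ρ the within-patient correlation. Both p and ρ are assumptions.
- Independent tests: P(at least one) = 1 − (1 − p)^k.
- Correlated tests (equicorrelated probit): P = 1 − E[(1 − Φ((c − √ρ·Z)/√(1 − ρ)))^k], with c = Φ⁻¹(p) and Z standard normal, integrated numerically.

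Percentage ever very low, 4 tests → 8 tests (ratio from unrounded values):

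| p | ρ = 0 | ρ = 0.5 | ρ = 0.7 | ρ = 0.9 |
|---|---|---|---|---|
| 2% | 7.8 → 14.9 (1.92) | 6.4 → 10.4 (1.63) | 5.3 → 7.9 (1.48) | 3.8 → 4.9 (1.28) |
| 5% | 18.5 → 33.7 (1.81) | 14.4 → 21.9 (1.52) | 12.0 → 16.8 (1.40) | 8.8 → 10.9 (1.23) |
| 10% | 34.4 → 57.0 (1.66) | 25.9 → 36.7 (1.42) | 21.7 → 28.8 (1.32) | 16.3 → 19.5 (1.19) |
| 15% | 47.8 → 72.8 (1.52) | 35.8 → 48.2 (1.35) | 30.3 → 38.7 (1.28) | 23.3 → 27.2 (1.17) |

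**Study-level effect**, at p = 10% and ρ = 0.7:
- 20% of patients full-length: 0.8 × 21.7 + 0.2 × 28.8 = 23.1%.
- 80% full-length: 0.2 × 21.7 + 0.8 × 28.8 = 27.4%.
- Three tests by Week 12 in everyone: 19.0%, whatever the mix.

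**Scale against a drug effect.** With 4 tests and ρ from 0.5 to 0.9, doubling p from 5% to 10% raises the percentage 1.8- to 1.9-fold (14.4 → 25.9, 12.0 → 21.7, 8.8 → 16.3). At p = 5%, doubling the tests raises it 1.2- to 1.5-fold. The two are about equal only if tests are independent (1.8 against 1.9).

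**The case against.** The case for leaving the plan alone has real weight.

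- **Many first occurrences should be early.** Protocol 8.1 says the maximum LDL-C reduction is usually reached by Week 4, and three of the eight scheduled tests fall within 12 weeks. Two earlier studies in Protocol Section 4 report similar rates of two consecutive values below 25 mg/dL: 19.5% in one reported to Week 52, and 18.3% in one with its endpoint at Week 24. Populations and definition differ from this trial, so this is weak evidence.
- **Repeat tests are unlikely to be independent.** At p = 5%, independence allows at most 7 × 0.05² = 1.75% of patients to have two consecutive very low values over 8 tests, far below those rates. Those patients had lower baseline LDL-C and perhaps a higher p, so this is only indicative. It favours the correlated columns.
- **Other outputs help.** Time to first occurrence, the dated listing, the exposure categories (SAP 2.4.3.1) and LDL-C by time point (SAP 2.4.4.2) will let a reader separate early from late occurrences.
- **The endpoint is descriptive.** It sits under additional efficacy analyses, is not an adverse event of special interest, and is not formally tested. Protocol Section 4 adds that no safety issue has been confirmed at these levels.

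These points limit the size but do not close the gap. The time-to-first display appears under cases only and the listing covers cases only, so neither counts patients who left early without a very low value. No planned output gives a cumulative incidence.

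A reader might go further and infer that the percentage reflects reimbursement timing as much as the drug, that follow-up inflates it about 2.5-fold, or that the starting-dose split is confounded. The documents support none of these. The first has no figure behind it. The second needs independent tests and a count of 3 against 8 (at p = 2%, 5.9% against 14.9%), which leaves out the short-stay patient's possible end-of-treatment test. The third holds only if dose or case mix varies with reimbursement timing.

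**Conclusion.** The concern holds in a limited form. The planned percentage depends on length of follow-up as well as on the drug effect, has no time reference, and may distort the two splits if dose or case mix differs between early- and late-reimbursing countries. The direction follows from the definition of the measure; the size does not. It rests on assumed per-test rates of 2% to 15%, an exchangeable correlation, a constant p over time and scheduled tests only. On that footing, 8 tests rather than 4 raise the figure about 1.2- to 1.6-fold at correlation 0.5 to 0.9, and at most about 1.9-fold under independence. If first occurrences cluster before Week 12, the true effect is smaller.

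**What to change.** In SAP 2.4.4.4, for both cut-offs, overall and by starting dose, add:

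1. The proportion of mITT patients with a very low value by Week 12, counted to the end of the Week 12 window (Day 98). SAP 2.3.1 already requires "Availability of the calculated LDL-C within the analysis window associated to Week 12", so follow-up is common to all of them. State that patients without a Week 12 value are outside this figure.
2. Kaplan-Meier cumulative incidence at Weeks 12, 24 and 48, censored at the end of the efficacy treatment period. Reading it at the ends of the analysis windows (Days 98, 182 and 357) avoids missing visits that fall just after the target day.

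Keep the crude percentage as secondary, define the observational period, which the SAP leaves undefined, and reconcile the two maximum durations (30 months is 30 × 365.25/12/7 ≈ 130 weeks, not 120).

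The cost is a few extra descriptive tables using a method already in the SAP. Kaplan-Meier will not correct for unscheduled testing, for the 24-week gaps between later lipid visits, or for the non-randomised choice of starting dose, and the table notes should say so.
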